4. OVERALL STUDY DESIGN

4.1. Study Design

This is a multicenter, open label study of Dara+Pom+Dex combined with ATRA in patients progressing on a Dara+Len+Dex regimen. The study is expected to enroll up-to a maximum of 42 patients (20-32 subjects previously exposed to Dara + Len + Dex; 10-22 subjects previously exposed to Dara + Pom + Dex)..

The phase 1b portion will follow a standard 3+3 dose escalation design with two dose levels and up to 12 patients. Under this design, the investigators will evaluate dose levels as follows:

- Dose level 1 - ATRA 35.5 mg/m²/day on days -2,-1 and 1 on a 28-day cycle in combination with daratumumab, pomalidomide, and dexamethasone
- Dose level 2 – ATRA 45 mg/m²/day on days -2,-1 and 1 on a 28-day cycle in combination with daratumumab, pomalidomide, and dexamethasone

During the dose-escalation phase and after the first cycle, and after the first cycle, patients who have not experienced a DLT, have not shown signs of PD, and in the opinion of the investigator would continue to benefit from treatment may receive additional cycles of treatment.

The phase 2 portion will be conducted in two stages. In the first stage, 10 patients will be accrued. A safety and efficacy analysis will be conducted 3 months after accrual of the first 10 patients. If there are 2 or fewer responses in these 10 patients, the study will be stopped due to futility. If the stopping rules for safety are met, then the study will be stopped due to toxicities. Otherwise, accrual will continue for a maximum of 42 in phase 1b and phase II combined.

During 28-day treatment cycles, patients will receive Dara 1800 mg subcutaneous (SC) at their current dose upon enrollment onto the study depending on their cycle. (If they are on cycles 1-2 then they will receive Dara 1800 mg SC days 1,8,15,22; if they are on cycles 3-6 they will receive Dara 1800 mg SC days 1 and 15; if they are on cycle 7 or beyond they will receive Dara 1800 mg SC on day 1).

Pomalidomide will be administered at the patient's currently tolerated dose (4,3, or 2 mg po daily) on days 1-21. For patients progressing on daratumumab, lenalidomide, and dexamethasone, the starting dose of pomalidomide will be 4 mg per standard of care.

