Dexamethasone will be administered at 40 mg once weekly on days 1,8,15 for patients 75 years old and younger and at 20 mg once weekly on days 1,8,15 for patients older than 75. Patients may stay on their currently administered steroid regimen if it does not match the above.

ATRA will be administered in a divided dose of twice daily as an oral formulation at 35.5 mg/m²/day for the phase 1b portion, then escalated to 45mg/m²/day for 3 days. The first administration of ATRA will be given in the morning, two days before the scheduled Dara infusion. The last administration of ATRA will

be given in the evening of the day that Dara was administered (days -2, -1, and 0; day 0 is the day of Dara infusion).

Treatment repeats every 28 days for at least 8 cycles in the absence of disease progression or unacceptable toxicity. Patients achieving stable disease may continue to receive treatment in the absence of disease progression or unacceptable toxicity.

After completion of the study treatment, patients are followed up at 28 days and then every 3 months for up to 12 months. Subjects will be evaluated for disease response during each cycle and at the end of study.

Adverse events (secondary endpoint) will be recorded and graded according to the National Cancer Institute Common Terminology Criteria for Adverse Events (NCI-CTCAE) (Version 5).

Tumor response, based on the investigator's assessment, will be evaluated according to the International Myeloma Working Group (IMWG) response criteria (Durie, 2006) and will be modified (mIMWG) to add criteria for MR (Kyle, 2009) (per Appendix B).

The phase 1b portion will estimate the maximum tolerated dose (MTD) by a standard 3+3 design using data collected in the dose escalation phase. MTD will be defined for each dosing level. A maximum of 2 dose levels are planned (35.5 mg/m²/day to 45 mg/m²/day). For phase 1b the maximum number of evaluable patients is planned to be 12.

The phase 2 portion will evaluate the clinical activity of Dara + Pom + Dex + ATRA. A Simon's two-stage minimax design will be used.

Analysis of biomarkers will also be explored in subjects who consent to participate in the exploratory biomarker study.

All subjects will be maintained on the Pomalidomide pregnancy prevention program (Appendix D) for the duration of the study.

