For all subjects who enroll into this study, study visits and serial measurements of safety and efficacy will be performed as outlined in Table 1, Table of Events. The overall study design is depicted in Figure 1.

[figure not shown]

Figure 1: Overall study design

Table 1: Table of events

	SCREENING	CYCLE 1					CYCLE 2+					END OF TREATMENT	FOLLOW UP
PROCEDURE	Day -28 to -1	Days -2, -1 (+/- 10 days)	Day 1 (+/- 10 days)	Day 8 (+/- 10 days)	Day 15 (+/- 10 days)	Day 22 (+/- 10 days)	Days -2, -1 (+/- 10 days)	Day 1 (+/- 10 days)	Day 8 (+/- 10 days)	Day 15 (+/- 10 days)	Day 22 (+/- 10 days)	28 days after last dose (+/- 28 days)	Q3 Months (+/- 28 days)
Informed Consent	X												
Inclusion/Exclusion Criteria	X												
Medical/Treatment History	X												
Vital Signs ^h	X	X	X	X	X		X	X	X	X	X	X	
Physical Exam	X	X	X	X	X		X	X	X	X	X	X	
Neurologic Exam	X		X					X					
Weight	X		X					X				X	
ECOG	X												
Patient reported outcomes – Quality of Life (QoL)	X		X					X				X	
PFT/FEV1 testing for patients with history of COPD/persistent asthma	X												
AE/SAE review		Continuous											
Medication evaluation	X	Continuous											
LOCAL LABS													
Venipuncture (Facility Fee)	X												
CBC (w/ platelet count)	X	X	X	X	X	X	X	X	X	X	X	X	
Serum Chemistry	X	X	X	X	X	X	X	X		X		X	
Hepatitis B (HBV) serology ^e	X												
HBV DNA testing ^f	X	Q12W during treatment, at the End of Treatment Visit, and Q12W for up to 6 months after the last dose of study treatment											
TSH, T3, Free T4, Coagulation	X												

	SCREENING	CYCLE 1					CYCLE 2+					END OF TREATMENT	FOLLOW UP
PROCEDURE	Day -28 to -1	Days -2, -1 (+/- 10 days)	Day 1 (+/- 10 days)	Day 8 (+/- 10 days)	Day 15 (+/- 10 days)	Day 22 (+/- 10 days)	Days -2, -1 (+/- 10 days)	Day 1 (+/- 10 days)	Day 8 (+/- 10 days)	Day 15 (+/- 10 days)	Day 22 (+/- 10 days)	28 days after last dose (+/- 28 days)	Q3 Months (+/- 28 days)
Thiamine testing	X		X					X					
Urinalysis	X												
Pregnancy Test	X		X					X					
Triglycerides	X		X	X	X	X		X	X	X	X		X
SPEP, UPEP, Serum/Urine Immunofix., Quant IgGs, 24Hr Urine, SFLC, B2 Micro	SOC		X					X					
CORRELATIVE SAMPLING													
Correlative Studies – peripheral blood collection, stool samples	X ^{b,d}	X ^{b,d}	X ^{b,d}					X ^{c,d}				X ^{c,d}	X ^{c,d}
Correlative Studies – bone marrow	X ^b	X ^b	X ^b									X	X ^c
CARDIOLOGY, PATHOLOGY, RADIOLOGY													
12-lead ECG	X ^g	X		X	X	X	X						
ECHO	X												

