7.4. Dose Escalation for ATRA and Study Stopping Rules

The phase 1b portion of the study will follow a 3+3 dose escalation design to evaluate Dose Level 1 (35.5 mg/m²/day) followed by Dose Level 2 (45 mg/m²/day) of ATRA in combination with Dara + Pom + dex for DLTs and to determine the MTD for further assessment in phase 2.

Patients will be enrolled in cohorts of 3 and assessed for DLTs over a 28-day period. In each dose level, the second and third patients can be dosed concurrently once the first patient in the cohort has gone uneventfully through the Day 8 visit. If it is necessary to enroll more than 3 patients in a cohort, and there have not been any TEAEs in the previously dosed patients in that cohort, these new patients can be enrolled concurrently.

If none of the patients in a cohort of 3 patients exhibits a DLT during the 28-day cycle, then the dose may be escalated for the next cohort of 3 patients. If 1 patient in a cohort of 3 patients exhibits a DLT, then that cohort will be expanded to a total of 6 patients. If 2 or more patients in a cohort of 3 patients exhibit a DLT, then that cohort will be deemed to have exceeded the MTD, and dose escalation will be stopped.

If the dose cohort below that at which the MTD is exceeded has enrolled only 3 patients, then 3 additional patients will be enrolled at that dose level. The MTD is defined as the highest dose with a cohort of 6 patients having no more than 1 patient with a DLT. For the cohort expansion, 3 patients will only be enrolled sequentially if a DLT observed in the initial cohort was life-threatening, it appeared before the Day 8 visit and/or the clinical team consider that based on the observed toxicity is prudent to stagger the enrollment. Sequential enrollment is not required in case of de-escalation or if no DLT was observed in the first 3 patients in a cohort.

During phase 1b dose escalation, patients who miss one or more scheduled Cycle 1 doses of ATRA for reasons other than a DLT will be replaced.

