Daratumumab Dosing Frequency	Dose Missed	Dosing Resumption
Every 2 weeks	>7 days	Next planned every-2-weeks dosing date
Every 4 weeks	>21 days	Next planned every-4-weeks dosing date

A missed dose will not be made up. Delay of Day 1 drug dosing in any given cycle should not result in a skipped dose but should lead to a delay of the entire cycle instead. A minimum of 4 days between daratumumab doses must be observed.

If a dose is delayed, then the dates of all subsequent doses must be adjusted. If a dose delay occurs, then blood samples should be collected on the actual day of study drug administration, not on the original scheduled drug administration day. Any adverse event deemed to be related to daratumumab that requires a dose hold of more than 28 days will result in permanent discontinuation of daratumumab, unless, upon consultation with the sponsor and the review of safety and efficacy, continuation is agreed upon.

Daratumumab Interruption or Missed Doses

A daratumumab dose that is held for more than the permitted time (Table 3) from the per-protocol administration date for any reason other than toxicities suspected to be related to daratumumab should be brought to the attention of the sponsor at the earliest possible time. Patients whose dose is delayed or missed for 3 or more consecutive doses should be withdrawn from study treatment, unless, upon consultation with the sponsor and the review of safety and efficacy, continued treatment is agreed upon.

Pomalidomide related toxicities

Table 4: Dose Modification Instructions for Pomalidomide

Toxicity ^a	Dose Modification
Neutropenia Grade 4 neutropenia (ANC < 500/ μ L) or Febrile neutropenia (ANC < 1,000/ μ L with a single temperature of > 38.5 °C or a sustained temperature of \geq 38 °C for more than one hour)	Withhold the dose and follow CBC weekly. If the subject was not receiving GCSF therapy, GCSF therapy may be started at the discretion of the treating physician. When dosing is resumed, the dose of POM may be maintained if neutropenia was the only POM-related toxicity requiring a dose modification and GCSF treatments are continued. Otherwise, decrease by one dose level. Note grade 4 neutropenia, ANC must be \geq 500/ μ L to restart dosing.

	For febrile neutropenia, ANC must be $\geq 1,000/\mu\text{L}$ to restart pomalidomide dosing at 1 mg less than the previous dose.

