7.6. Criteria for Discontinuing ATRA and Discontinuation from Study

ATRA should be discontinued in patients experiencing an AE in Cycle 1 meeting criteria for a DLT for which the investigator considers that retreatment of the patient could be dangerous. For Grade 4 life threatening TEAEs, the subject will be permanently withdrawn from study, except when the investigator determines that the patient is receiving clinical benefit and there are chances to provide supportive care to mitigate the Grade 4 event to recur. In these circumstances, treatment may be restarted at the previously safe dose level or below when toxicity recovers to Grade ≤ 1 or baseline.

If the next cycle of treatment is delayed for > 21 days because of ATRA-related toxicities, then the patient should have study treatment discontinued unless the investigator considers that the patient will receive benefit continuing in the study. If treatment discontinuation is determined, the end of study visit should be completed within 30-40 days after the last administration of ATRA.

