APPENDIX A: Research Biospecimen Sample Collection

Code for Correlative Studies	(PtID) (Timepoint) (Date)
Peripheral Blood Samples (7x Yellow top tubes (BD Vacutainer ACD Solution A Blood Collection tubes – 8.5ml) – 59.5ml 1 Streck Cell-Free DNA BCR tube	Timepoint ID
Screening/Cycle 1 Day 1 - to be collected prior drug administration	1
Cycle 2 Day 1 (+/-2 days)	2
End of Treatment Visit	EOT
Relapse	4 R
All Peripheral blood samples are to be kept at room temperature – no immediate processing needed.	
Samples for HackensackUMC subjects are to be delivered via courier to lab. If sample is collected in the late afternoon, please store at room temperature on a shaker (slow speed) until delivered to [name] the next day.	
Samples for Georgetown University subjects are to be shipped via Fed Ex on the day of collection. The tubes are to be banded in sealed plastic bag and wrapped in bubble wrap. If sample is collected in the late afternoon, please store at room temperature on a shaker (slow speed) until next shipment day.	

Please ship to: [name] Center for Discovery & Innovation, Hackensack Meridian Health [name] [contact] e-mail: [contact]
	
Any time patients receive antibiotics while on study they should have stool and peripheral blood collected before starting antibiotics and upon completion of antibiotics (within a 7 day window).	

Bone Marrow Aspirate Samples	Timepoint ID
(1x Yellow top tube) – first pull about 4 ml	
Screening Visit or day 1, Cycle 1	S
Cycle 2 Day 1 (+/- 2 days)	2
End of Treatment Visit or Relapse	EOT
All Bone Marrow Aspirate samples are to be kept at room temperature – no immediate processing needed.	
Samples for HackensackUMC subjects are to be delivered via courier to lab. If sample is collected in the late afternoon, please store at room temperature on a shaker (slow speed) until delivered to [name] the next day.	
Samples for Georgetown University subjects are to be shipped via Fed Ex on the day of collection. The tubes are to be banded in sealed plastic bag and wrapped in bubble wrap. If sample is collected in the late afternoon, please store at room temperature on a shaker (slow speed) until next shipment day.	

Please ship to: [name] HMH Center for Discovery & Innovation [name] [contact] e-mail: [contact]
	

Stool Samples	Timepoint ID

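### Table 1's ±10-day windows exceed the 7-day visit spacing, thin laboratory DLT monitoring in Cycle 1, and conflict with the ATRA timing, Table 3 and Appendix A

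*Combined protocol and SAP*

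**What the plan says.** - **Table 1 (Section 4.1).** Every Cycle 1 and Cycle 2+ column (Days -2/-1, 1, 8, 15, 22) is headed with ±10 days; the lead-in column reads "Days -2, -1 (+/- 10 days". These columns hold the blood count, chemistry and ECG rows and also the ATRA and daratumumab rows. No footnote limits the tolerance to assessments.
- **Spacing.** For patients in daratumumab cycles 1-2, Section 4.1 states that "they will receive Dara 1800 mg SC days 1,8,15,22", so the visits are seven days apart.
- **ATRA timing.** Section 4.1: "The first administration of ATRA will be given in the morning, two days before the scheduled Dara infusion". Section 7.5 repeats this.
- **Daratumumab tolerance.** Section 7.5 and Table 3 count a within-cycle dose as missed when it is more than 3 days late (weekly), 7 days late (every two weeks) or 21 days late (every four weeks). Cycle Day 1 is excepted: a delay there moves the whole cycle. In addition, "A minimum of 4 days between daratumumab doses must be observed".
- **Stagger and DLT period.** Section 7.4 lets patients 2 and 3 be dosed "once the first patient in the cohort has gone uneventfully through the Day 8 visit", and sets 28 days of DLT assessment. Section 7.3 ends the DLT period at Cycle 2 Day 1 dosing.
- **Research samples.** Appendix A has "Cycle 2 Day 1 (+/-2 days".
- **End of treatment.** Table 1 has "28 days after last dose (+/- 28 days". Section 5.2 collects adverse events until 30 days after treatment stops. Section 7.6 says "the end of study visit should be completed within 30-40 days after the last administration of ATRA".

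**The concern.** A visit window is meant to absorb scheduling noise without changing the order or rough spacing of the visits. A tolerance of ten days on visits seven days apart cannot do that.

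Phase 1b depends on this timing. Several DLTs in Section 7.3 are laboratory findings: Grade 4 thrombocytopenia however brief, Grade 4 neutropenia persisting beyond a week, and transaminase elevations judged by whether they settle within 7 days. In a 3+3 design one DLT among three patients expands the cohort and two stop escalation, so a single undetected event can change the dose decision. The study also tests whether ATRA given shortly before daratumumab restores sensitivity, and the lead-in column carries the same loose window. Section 7.4 replaces patients who miss a Cycle 1 ATRA dose for reasons other than a DLT, so what counts as on schedule also affects who is evaluable.

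**Working it through.** The plan states no figure to reproduce. The inputs are the nominal days and the ±10 days from Table 1, the limits in Table 3, and the 4-day minimum in Section 7.5. Days are counted continuously; if there is no Day 0, dates on the far side of Day 1 shift by one.

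**1. Windows (nominal day ± 10).**

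| Visit | Earliest | Latest |
|---|---|---|
| Days -2/-1 | -12 | 9 |
| Day 8 | -2 | 18 |
| Day 15 | 5 | 25 |
| Day 22 | 12 | 32 |
| Cycle 2 Day 1 (nominal Day 29) | 19 | 39 |

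Day 1 of Cycle 1 is treated as fixed, because Section 5.1 defines it as the start of dosing. Its own ±10 days has no clear meaning.

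**2. Overlap.** For visits on nominal days d and d + 7, the shared calendar days are (d + 10) - (d + 7 - 10) + 1 = 14. No overlap requires 2w < 7, so the widest symmetric whole-day window is w = 3.

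**3. Longest gap between adjacent weekly visits.** 7 + 10 + 10 = 27 days. A compliant, ordered example: Day 1; the Day 8 visit on Day 2, 3 or 4; the Day 15 visit on Day 5; the Day 22 visit on Day 32. Days 6 to 28 (23 of the 28 DLT days) then have no scheduled blood count. If weekly daratumumab is given and the 4-day minimum is kept, the Day 15 visit cannot precede Day 9, and this gap becomes 32 - 9 = 23 days. With ±3 days the longest gap would be 7 + 3 + 3 = 13 days.

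**4. DLT period.** The earliest Cycle 2 Day 1 is 29 - 10 = Day 19. Days 1 to 18 give 18 days of observation under Section 7.3, against 28 in Section 7.4.

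**5. Stagger.** With visits in order on separate days, the Day 8 visit can fall on Day 2, one day after Day 1.

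**6. ATRA.** The lead-in window closes at -1 + 10 = Day 9, after the Day 1 daratumumab dose that ATRA must precede by two days.

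**7. Table 1 against Table 3 (late side).**

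| Schedule | Missed if later than | Delays allowed by Table 1 but missed by Table 3 |
|---|---|---|
| Weekly | 3 days | 4 to 10 days |
| Every 2 weeks | 7 days | 8 to 10 days |
| Every 4 weeks | 21 days | none (10 < 21) |

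**8. Appendix A.** ±2 days against ±10 days for Cycle 2 Day 1 samples.

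**9. End of treatment.** 28 ± 28 gives 0 to 56 days after the last dose. Blood count and chemistry are not scheduled in the follow-up column, so the last of each may fall on Day 0 while adverse events are collected to Day 30.

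**The case against.** The best defence is that other text governs. Section 4.1 fixes ATRA relative to daratumumab, and Section 7.5 names Table 3 as the window for within-cycle doses. Adverse-event review is continuous, Table 4 requires weekly blood counts after a Grade 4 cytopenia, and escalation needs 28-day assessment and a review of all patients' safety data. No sensible site would start Cycle 2 on Day 19 while pomalidomide runs to Day 21.

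Much of this limits the point without removing it. Table 4 starts only once the cytopenia has been found, and continuous review does not reveal an asymptomatic one. That dosing text elsewhere is stricter shows that Table 1 needs correcting.

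Several stronger readings are tempting, and the documents do not support them:
- **Cycle 1 could pass unmonitored.** Each visit must still occur and adverse-event review continues.
- **The Day 8 condition could be met before dosing.** The arithmetic allows Day -2, but a patient cannot pass uneventfully through a visit before treatment. The fair criticism is that no minimum time on treatment is stated.
- **Table 1 contradicts all of Table 3.** The every-four-week row and cycle Day 1 are not in conflict.
- **Myeloma panels could be 8 to 48 days apart (28 ± 20), which would damage response confirmation.** A delayed Day 1 moves the later doses. Re-anchored, the range is 28 ± 10, or 18 to 38 days. Appendix B asks for two consecutive assessments at any time before new therapy, with no fixed interval.
- **The end-of-treatment window contradicts Section 7.6 outright.** That visit is timed from the last ATRA dose, Table 1's from the last dose, and the ranges overlap.
- **Appendix A cannot be met.** A site keeping ±2 days satisfies both.

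**Conclusion.** The windows are wrong as written. They overlap by 14 days between adjacent weekly visits and permit up to 27 days between scheduled blood counts in Cycle 1 (23 for the same pair of visits when weekly daratumumab keeps its 4-day minimum). They also allow DLT observation to end after about 18 days on the Section 7.3 definition, and they leave the Day 8 release of patients 2 and 3 without a minimum exposure. The conflict with dosing text covers weekly and every-two-week daratumumab and the ATRA lead. The mismatches with Appendix A and at end of treatment are secondary.

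These are limits of what Table 1 permits, not forecasts of site behaviour. They assume Cycle 1 Day 1 is fixed, visits occur in order on separate days, and the column windows apply as printed. Within those limits, detection of laboratory DLTs is weakened, and dose escalation depends on that detection.

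**What to change.** Amend Table 1 so that windows for assessments (visits, blood count, chemistry, ECG) are shorter than the spacing and do not overlap. At seven-day spacing that means at most ±3 days. This is an arithmetic ceiling: it still allows 13 days between counts, so the sponsor may want less where a DLT is defined by a duration of about a week. State that the ±10 days does not apply to dosing.

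Then reconcile:
- the ATRA and daratumumab columns with Sections 4.1 and 7.5 and Table 3;
- the Day 8 stagger and the DLT period between Table 1, Section 7.3 and Section 7.4;
- Cycle 2 Day 1 sampling with Appendix A;
- the end-of-treatment window with the 30-day adverse-event period in Section 5.2 and the separately anchored visit in Section 7.6.

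Which dosing and stagger rule holds is for the sponsor to decide. The cost is an amendment to Table 1 and the matching text, less scheduling flexibility, and some more minor window deviations.

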2. STUDY OBJECTIVES

Primary Objectives:

Phase 1b: To determine the safety and toxicity profile of the combination of Dara + Pom + Dex + ATRA.

Phase 2: To determine the ORR of the combination of Dara + Pom + Dex + ATRA in patients progressing on Dara + Len + Dex

Secondary Objectives:

- 1) To determine the ORR of the combination of Dara + Pom + Dex + ATRA in patients progressing on Dara + Pom + Dex
- 2) To determine the best stringent complete response (sCR)/CR/near CR (nCR) and >/= very good partial response (VGPR) rates.
- 3) To estimate time on study (TOS), duration of response (DOR), time to progression (TTP), progression-free survival (PFS) and overall survival (OS) distributions.
- 4) To define the toxicity using CTCAE V5 criteria.
- 5) To evaluate the status of minimal residual disease (MRD) in patients who achieve sCR, CR, or nCR.
- 6) To evaluate prognostic markers and markers of response to the combinations in patients by analyzing pre and post-treatment clinical covariates and immune cell subsets as well as gene expression profiling.
- 7) To determine prognostic factors for PFS and OS.

Exploratory Objectives

- 1) To identify predictive factors for clinical response to Dara in combination with ATRA, Pom, and Dex.
- 2) To identify risk factors for Dara in combination with ATRA, Pom, and Dex- induced immune-related adverse events.
- 3) To correlate immune profiles (baseline, on-treatment, end of treatment, remission or PD) with ORR/PD.
- 4) To determine if any peripheral blood laboratory values during patient's routine clinical care are associated with ORR/PD or risk for treatment-related adverse events.
- 5) To correlate molecular profiles (baseline, on-treatment, end of treatment, remission or relapse) with ORR/PD.
- 6) To identify intestinal microbiota associated biomarkers that predict response and risk for development of treatment-related toxicities at baseline, on-treatment, post-treatment and relapse.

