3. STUDY ENDPOINTS

Primary Endpoints:

Phase 1b: The percentage of patients with treatment emergent adverse events (TEAEs) overall and per dose level.

- Patients with DLTs at each dose level.
- Patients with Grade ≥ 3 TEAEs
- Patient with serious adverse events (SAEs)
- Patients who discontinue because of TEAEs
- Patients with dose modifications (delays, interruptions, dose reductions)
- Clinically significant laboratory values

Phase 2: ORR as defined by IMWG criteria (subjects progressing on Dara + Len + Dex)

Secondary Endpoints:

- 1) ORR as defined by IMWG criteria (subjects progressing on Dara + Pom + Dex)
- 2) Rate of CR, sCR, or nCR
- 3) Rate of VGPR
- 4) TTP
- 5) DOR
- 6) PFS using Kaplan Meier
- 7) OS using Kaplan Meier

Exploratory Endpoints:

Explorative endpoints of samples collected before, during and after treatment with Dara + ATRA, + Pom + Dex and include but are not limited to the following:

- 1) Gut Microbiome analysis
- 2) Immune cell subset analyses
- 3) Analyses of cytokine, chemokine, inflammatory/anti-inflammatory and bacterial translocation markers
- 4) Basic peripheral blood laboratory variables
- 5) Genetic and epigenetic profiles

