All-trans retinoic acid (ATRA) has been shown in both cell lines and primary MM samples to increase CD38 expression levels and also to reduce expression of the complement-inhibitory proteins CD55 and CD59 (Nijhof et al, 2015). This resulted in significant enhancement of activity of Daratumumab in vitro and in humanized MM mouse models. Daratumumab and ATRA exhibit a strong synergy in MM cells derived from Dara-naïve patients and from patients with Dara-refractory disease, providing preclinical rationale for further evaluation of Daratumumab combined with ATRA in MM patients. Preliminary data from phase 1 trials combining Daratumumab and ATRA have shown that the combination is safe using ATRA 45 mg/m²/day dose.

Second primary malignancies will be monitored as events of interest and will be reported as a serious adverse event (SAE) regardless of causal relationship to investigational product (IP). The multicenter nature as well as the inclusion of patients in Japan of the study provides reassurance that the results are likely to have general applicability and the size of the study allows accurate description of the nature, frequency, and severity of the AE profile. Subjects will receive study treatment until PD or discontinuation. In studies evaluating agents for subjects with refractory MM or relapsed and refractory progressing or relapsed malignant diseases, it is common practice to continue study treatment until PD or intolerable toxicity develops. All subjects will be followed for OS, subsequent anti-myeloma therapies and SPMs.

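### Table 1 schedules no myeloma protein panel after treatment ends, so progression is not scheduled to be measured in patients who stop without PD

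*Combined protocol and SAP*

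**What the plan says.** - **Table 1 is the schedule for efficacy.** Section 4.1 states that for all enrolled subjects "study visits and serial measurements of safety and efficacy will be performed as outlined in Table 1, Table of Events".
- **The panel row.** The row "SPEP, UPEP, Serum/Urine Immunofix., Quant IgGs, 24Hr Urine, SFLC, B2 Micro" is filled at Screening (as standard of care), Cycle 1 Day 1 and Cycle 2+ Day 1. The End of Treatment and Follow-up (every 3 months) cells are empty.
- **Response evaluation.** Section 4.1, repeated in the Protocol Summary and section 7.5, states: "Subjects will be evaluated for disease response during each cycle and at the end of study".
- **Follow-up visits.** The same places state: "After completion of the study treatment, patients are followed up at 28 days and then every 3 months for up to 12 months".
- **Endpoints.** The third secondary objective in section 2 is "To estimate time on study (TOS), duration of response (DOR), time to progression (TTP), progression-free survival (PFS) and overall survival (OS) distributions". Section 3 lists TTP, DOR and "PFS using Kaplan Meier" as secondary endpoints.
- **Leaving treatment.** Section 4.2 states: "Subjects will receive study treatment until PD or discontinuation". Sections 7.5 and 7.6 give routes off treatment other than PD: three or more consecutive delayed or missed daratumumab doses, Grade 4 life-threatening events, and cycle delays of more than 21 days for ATRA toxicity, each with exceptions.
- **Progression and response.** In Appendix B, PD is chiefly a 25% rise from the lowest value in serum or urine M-component, or in the free light chain difference where those are not measurable. Response categories need two consecutive assessments before any new therapy.

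**The concern.** The text promises a response evaluation at the end of study and names three endpoints that depend on dating progression. The schedule that governs efficacy measurements carries the necessary tests only while the patient is on treatment. The visits themselves exist: triglycerides have an entry at follow-up and blood counts have one at End of Treatment. Only the tests that define progression are absent.

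At stake is how PFS, TTP and DOR are built for patients who leave treatment before progressing. Either their progression dates come from whatever testing each site happens to do, or they are censored at some on-treatment date. If stopping is related to prognosis, as is plausible when the reason is toxicity, Kaplan-Meier's assumption of independent censoring is doubtful. With at most 42 patients, and DOR confined to responders, a few such patients can move the curves.

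**Working it through.** There is no stated figure to reproduce. The check sets Table 1 against the text.

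**1. Are the blanks real?** The table has one label column and 13 visit columns. The panel row splits into 14 cells, matching the header, with entries at Screening, Cycle 1 Day 1 and Cycle 2+ Day 1. Other rows split the same way and reach the later columns: weight and blood counts have an End of Treatment entry, triglycerides a Follow-up entry, and correlative blood and stool both. A text-extraction fault is therefore unlikely.

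**2. How many visits are concerned?** Section 4.1 gives one visit at 28 days, then one every 3 months for up to 12 months: 1 + 12/3 = up to 5 post-treatment visits. The panel is marked at none. Section 4.3 counts the 12 months from enrollment instead, which would leave fewer visits but still no panel.

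**3. Does anything else scheduled fill the gap?**

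| Item after treatment | Why it does not date progression |
|---|---|
| Radiology | Listed only at screening, as standard of care |
| Clinical bone marrow at Follow-up | At investigator discretion (footnote i); marrow percentage counts for PD only without measurable serum, urine or FLC disease |
| Blood count and chemistry at End of Treatment | Can suggest clinical relapse, which Appendix B keeps out of TTP and PFS |
| Physical examination at End of Treatment | Helps only if progression shows as a detectable lesion |
| Correlative samples at relapse (footnote c, Appendix A) | Presume that relapse has already been identified |
| Follow-up items named in section 4.2 | OS, later therapies and second malignancies; progression is not named |

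**4. Who is exposed?**
- Stopped because of PD: the event is already found on the Day 1 tests. Not exposed.
- Died: captured through OS follow-up, so the death component of PFS remains.
- Stopped without PD, alive: no scheduled test for later progression. Exposed for PFS, TTP and, in responders, DOR.
- Response first seen at the last Day 1 test: no scheduled second assessment. This is the only route by which ORR is touched.

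**5. Which way could the bias go?** No censoring rule appears in section 9.3, and section 9.1 leaves detailed methods to the statistical analysis plan. Two routes favour the regimen: censoring patients whose outlook is worse than that of those remaining, and finding progression late because nobody was scheduled to look. One route goes the other way: if sites test only patients who appear to be relapsing and the rest are censored early, events are over-represented. Favourable bias is the more likely result, but it is not demonstrated.

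**The case against.** The strongest reply is that most patients should be treated until progression. Section 4.2 says so, and section 4.1 reads "Treatment repeats every 28 days for at least 8 cycles in the absence of disease progression or unacceptable toxicity", which is a minimum. Such patients are tested every cycle and their events are observed. This stands, and it limits the point to patients who stop without PD.

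A reader might treat eight cycles as a planned end of treatment and use the median PFS figures cited in the protocol to work out how many patients would still be progression-free then. The documents do not support that step. Eight cycles is not a stopping point, and the share progression-free at a given time is not the share who stop without PD and later progress unseen.

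A reader might also infer that PFS, TTP and DOR are wholly unobserved after treatment. That too goes beyond the documents. Deaths are captured, a marrow may be done at discretion, the relapse samples presume that relapse is recognised, and routine care may find some progressions. The accurate statement is that progression is not scheduled to be measured.

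On confirmation, Appendix B accepts a second assessment at any time before new therapy, so an unscheduled test could serve. This also stands; the gap is that none is planned.

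Finally, the response-evaluation sentence in section 4.1 promises evaluation each cycle and at the end of study, not at each 3-month visit. That is correct. The quarterly tests have to be justified by the PFS, TTP and DOR endpoints rather than by that sentence.

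**Conclusion.** The point holds for patients who stop treatment without PD. Table 1 and the end-of-study evaluation in section 4.1 do not agree, and up to five post-treatment visits carry no test able to detect the main forms of progression in Appendix B. For these patients PFS, TTP and DOR depend on unscheduled testing or on censoring that may be informative, probably in the favourable direction. A response first seen at the final Day 1 test has no planned confirmation.

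The size of the effect cannot be derived, because the documents do not give the share of patients who stop without PD. The affected endpoints are secondary, and most of the primary ORR is unaffected. Two conclusions a reader might draw are not established: that these patients will be censored at their last on-treatment test, since no such rule is written, and that the estimates are certainly biased upward. The change is still worth making, because tests not done at the visit cannot be recovered later.

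**What to change.** 1. In Table 1, mark the existing serum, urine and FLC panel at End of Treatment, to match the end-of-study evaluation in section 4.1.
2. Mark the same panel at the already scheduled 3-month follow-up visits until progression or new anti-myeloma therapy, to support PFS, TTP and DOR.
3. State in section 9.3 or the statistical analysis plan how patients who stop without PD are censored for PFS, TTP and DOR, including what happens when new therapy starts.
4. Say which visit the end-of-study evaluation refers to, and reconcile the 12-month follow-up in section 4.1 (after treatment) with that in section 4.3 (after enrollment).

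The cost is a few extra routine laboratory tests per patient at visits already planned. Item 3 costs only text; without items 1 and 2 it would make the limitation explicit but would not supply the missing measurements.
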